13.6.4.1 TDT Population

Hematological Improvement Endpoints

Hematological improvement is defined as a $\geq 20\%$, $\geq 33\%$, or a $\geq 50\%$ reduction in pRBC units transfused, with a reduction of at least 2 units of RBCs, measured over a fixed period of 12 weeks (from Week 12 to Week 24 and from Week 24 to Week 36) or over 24 weeks (from Week 12 to Week 36) as compared to the 12-week period prior to the Baseline (Day 1) visit. The pRBC units are defined as the sum all pRBCs units for the specific 12- or 24-week period.

Hematological improvement will also be assessed using any 12-week rolling time period – Day 2 to 85, Day 3 to 86, etc. through Day 170 to Day 253 (Week 36) – compared to the 12 weeks prior to Baseline (Day 1) – and any 14-week rolling time period – Day 2 to 99, Day 3 to 100, etc. through Day 156 to Day 253 (Week 36) – compared to the 12 weeks prior to Baseline (Day 1). For the rolling time periods, a responder is defined as a subject who meets the hematological improvement criteria in at least one of the rolling time periods.

The proportion of subjects with a $\geq 20\%$ hematological improvement (a 20% or more reduction in pRBC units transfused, with a reduction of at least 2 units of RBCs) during Week 12 to Week 24 and Week 24 to Week 36, compared to the 12-week prior to Baseline (Day 1) timeframe, will be assessed using a CMH test. The estimate of the odds ratios and the associated 95% confidence intervals (CIs) and p-values from the CMH tests will be presented for each active arm vs. placebo at each timepoint. The difference in proportions (each active arm-Placebo and the combined active arms-Placebo) and corresponding 95% CI will be also provided. An odds ratio exceeding 1 indicates that the proportion of improved subjects in the treated arm is higher than in the placebo arm.

The proportion of subjects with a $\geq 33\%$ hematological improvement and the proportion of subjects with a $\geq 50\%$ hematological improvement for the Week 12 to Week 24 and Week 24 to Week 36 time periods will be analyzed similarly as for the proportion of subjects with $\geq 20\%$ hematological improvement.

The above analyses for the proportions of subjects with $\geq 20\%$, $\geq 33\%$, $\geq 50\%$ hematological improvement will be repeated for the 24-week post-Baseline time period, Week 12 to Week 36.

The proportion of subjects with a $\geq 20\%$, $\geq 33\%$, and $\geq 50\%$ hematological improvement for the 12-week rolling and 14 week rolling time periods will be analyzed similarly as for the fixed time periods above.

Bar plots will be provided. The proportion of subjects with a $\geq 20\%$, $\geq 33\%$, and $\geq 50\%$ hematological improvement, odds ratios, 95% CIs, and p-values will be displayed by treatment arm for Week 12 to Week 24, Week 24 to Week 36, and Week 12 to Week 36, compared to the 12-week period prior to Baseline (Day 1). Separately, bar plots will be provided for the 12 week rolling time periods and for the 14 week rolling time periods.

Number of Transfusion Events Endpoint

The number of transfusion events in IMR-687 arms from Baseline to Week 36 compared to placebo will be assessed using an ANCOVA model with baseline value as a covariate and treatment as a factor. Summary statistics of the number of cumulative transfusions at every 12 weeks post-Baseline from Week 12 through Week 36 will be presented. All post-baseline assessments of number of transfusions will be cumulative from baseline. For example, the number of transfusions at Week 24 and Week 36 will include all transfusions from baseline through the Week 24 and Week 36 visits, respectively. The least squares mean (LSMean) estimates and 95% CIs will be presented for each active arm, the combined active arms, and placebo at Week 36. Additionally, the LSMean difference estimates and associated 95% CIs and p-values at Week 36 will also be reported for each active arm vs. placebo and the combined active arms vs. Placebo.

Box whisker plots of the mean number of transfusion events, mean number of units, and mean pre-transfusion Hb with outliers over time will be provided by time periods (Weeks 1-12, Weeks 13-24, and Weeks 25-36) by treatment arm.

Transfusion events data will be reported in a by-subject listing using the ITT Analysis Set.

Iron Chelation Therapy Endpoints

The mean changes from Baseline to Week 36 for iron chelation therapy daily (ICT) dose will be assessed using ANCOVA models with baseline value as a covariate on the Safety Analysis Set. The Baseline mean daily dose of ICT will be calculated during the 12 weeks prior to the first dose of study drug. The post-baseline (Week 36) mean values will be calculated during the last 12 weeks of the 36-week treatment period, or the last 12 weeks of study drug for subjects who are discontinued early. Summary statistics for observed values at Baseline and Week 36 and change from Baseline to Week 36 of ICT will be presented. The change from baseline in mean daily dose of ICT at Week 36 will be analyzed using an ANCOVA model with baseline ICT mean daily dose as a covariate, including only subjects who did not change their ICT drug from Baseline to post-baseline and used only one ICT drug. LSMean estimates and 95% CIs will be presented for each active arm and placebo at Week 36. The LSMean difference estimates and associated 95% CIs and p-values at Week 36 will also be reported for each active arm vs. placebo and the combined active arms vs. Placebo. The values at Week 24 will be analyzed in a similar manner. Line plots will be provided for mean change from Baseline with 95% CI to Week 36 for ICT daily dose by treatment arm.

The number and percentage of subjects who took monotherapy (i.e., only one ICT drug) vs. combo therapy (i.e., more than one ICT drug) will be summarized at Baseline and Week 36, by treatment arm. The percent change in mean daily dose of ICT from Baseline to Week 36 will be summarized with descriptive statistics, by treatment arm.

For subjects that are stable on the same ICT drug(s) throughout the study, the change in mean daily dose will be calculated. Subjects who switched drugs during the study will be excluded. For subjects on more than one drug, the change will be averaged for the drugs.

Serum Ferritin Endpoint

The mean changes from Baseline to Week 36 for serum ferritin will be assessed using ANCOVA models with baseline value as a covariate on the Safety Analysis Set. The Baseline mean serum ferritin will be calculated during the 12 weeks prior to the first dose of study drug. The post-baseline (Week 36) mean values will be calculated during the last 12 weeks of the 36-week treatment period, or the last 12 weeks of study drug for subjects who are discontinued early. Summary statistics for observed values at Baseline and Week 36 and change from Baseline to Week 36 of serum ferritin will be presented. The change from baseline in mean serum ferritin at Week 36 will be analyzed using an ANCOVA model with baseline serum ferritin mean as a covariate. LSMean estimates and 95% CIs will be presented for each active arm and placebo at Week 36. The LSMean difference estimates and associated 95% CIs and p-values at Week 36 will also be reported for each active arm vs. placebo and the combined active arms vs. Placebo. Line plots will be provided for mean change from Baseline with 95% CI to Week 36 for serum ferritin by treatment arm. The values at Week 24 will be analyzed in a similar manner.

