Mean change from Baseline in mean HbF values at Weeks 12 to 24 and Weeks 24 to 36 in the absence of transfusions.		X	
Proportion of subjects with an increase from Baseline of $\geq 3\%$ in mean HbF values at Weeks 12 to 24 and Weeks 24 to 36 in the absence of transfusions.		X	
Exploratory Endpoints		TDT	NTDT
The PD effects of IMR-687 from Baseline to Week 36, as measured by the mean change from Baseline in serum PD markers of erythropoiesis, iron metabolism, and hemolysis.	X	X	
Mean change in transfusion burden expressed as units of RBCs as a continuous variable during Week 12 to Week 24, Week 24 to Week 36, and Week 12 to Week 36, compared to the 12 weeks prior to Baseline (Day 1).	X		

The proportion of subjects who are transfusion independent for ≥ 8 weeks during treatment.	X	
Mean change from Baseline in TranQOL quality of life tool at Weeks 12, 24, and 36.	X	
Mean change from Baseline in SF-36 quality of life tool at Weeks 12, 24, and 36.	X	X
Pharmacogenomic analyses of genes that may affect treatment response (including α -globin, gamma-globin Xmn1 polymorphism, and BCL11A).	X	X
Proportion of subjects who have an Hb increase of ≥ 1.0 g/dL from Baseline for ≥ 14 days in the absence of RBC transfusions.		X
Proportion of subjects who are RBC transfusion-free over 36 weeks and other variables of transfusion burden.		X
Duration of the mean Hb increase from Baseline of ≥ 1.0 g/dL over 36 weeks.		X
Proportion of subjects who have an increase from Baseline ≥ 1.5 g/dL in mean of Hb values at Week 24 and Week 36 compared to Baseline in the absence of transfusions.		X
Mean number of transfusion events from Baseline to Week 24.	X	
Mean change from Baseline in NTDT-PRO tiredness/weakness (T/W) domain score over a continuous 12-week interval from Week 12 to Week 24 and Week 24 to Week 36.		X
Mean change from Baseline in NTDT-PRO total score and T/W domain score at Week 24 and Week 36.		X
Mean change in biomarkers from Baseline to Week 36, stratified by genotype. ^a	X	X
Time to first Hb increase (≥ 1.0 g/dL)		X

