10.1.6 Red Blood Cell Transfusion Reduction: 24-Week Fixed Interval

Transfusion burden will also be measured using a “fixed” 24-week time interval. The 24-week intervals used for analysis are defined as below.

Pre-treatment 12-week interval: from Day -83 to Day 1;

Week 13–36 interval: from Day 86 to Day 253.

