13.6.6 Exploratory Efficacy Analyses

The PP Analysis Set will be used for all exploratory efficacy endpoint analyses. Selected analyses will be repeated on the ITT and/or mITT Analysis Sets as sensitivity analyses.

Table 11 Exploratory Endpoints – TDT Population

Exploratory Endpoints	Time Points	Exploratory Endpoint Analysis
The PD effects as measured by the mean change from Baseline in serum PD markers of erythropoiesis, iron metabolism, and hemolysis.	Baseline to week 36 (including all visits in between)	Mixed Model Repeated Measures (MMRM) analysis: Mean (95% CI), Mean difference (95% CI), and p-value will be provided.
Mean change in transfusion burden (pRBC units) as a continuous variable	Week 12 to Week 24, Week 24 to Week 36, and Week 12 to Week 36, compared to the 12-week prior to Baseline (Day 1)	Descriptive summary
Proportion of subjects who are transfusion-free (independent) for ≥ 8 weeks during treatment	Over treatment time	CMH analysis: Odds ratios (active arm vs. placebo), 95% CI, p-value, difference in proportions (active arm-Placebo) and corresponding 95% CI will be provided
Proportion of subjects who are RBC transfusion-free (independent) over 36 weeks and other variables of transfusion burden	Over 36 weeks	CMH analysis: Odds ratios (active arm vs. placebo), 95% CI, p-value, difference in proportions (active arm-Placebo) and corresponding 95% CI will be provided
Mean number of transfusion events	Baseline to Week 36	
 Summary statistics of the number of cumulative transfusions at every 3 weeks post-Baseline from Week 3 through Week 36. Analysis of Covariance (ANCOVA) analysis with Baseline value as a covariate: LSMean (95% CI), LSMean difference (95% CI) between each active dose and placebo, and p-value. Plots of the mean number of transfusions, mean number of units, and pre-transfusion mean Hb over time
Change from Baseline in mean pre-transfusion Hb values at Weeks 12 to 24, Weeks 24 to 36, and Weeks 12 to 36 [using pre-transfusion Hb from the Historical Transfusion Burden and the Transfusion Burden CRFs]	Baseline to Week 12 to Week 24, Week 24 to Week 36, and Week 12 to Week 36	
 Summary statistics for the Baseline, post-Baseline, and change from Baseline Hb by treatment arm Scatter box-whisker plots for mean change over continuous 12-week and 24-week intervals ANCOVA analysis with Baseline value as a covariate: LSMean (95% CI), LSMean difference (95% CI), and p-value.

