13.6.6.1 TDT Population

PD Effects of Erythropoiesis, Iron Metabolism, and Hemolysis Endpoints

The mean changes from Baseline in serum PD markers of erythropoiesis, iron metabolism, and hemolysis will each be analyzed with an ANCOVA model with the corresponding Baseline value as a covariate. LSMean estimates and 95% CIs will be presented for each active arm and placebo at Week 36. The

LSMean difference estimates and associated 95% CIs and p-values at Week 36 will also be reported for each active arm vs. placebo and the combined active arms vs. Placebo.

Transfusion Burden Endpoints

Summary statistics of transfusion burden during the 12-week period prior to Baseline (Day 1) and the 24-week post-Baseline time period will be provided.

Boxplots illustrating the observed pRBC of transfused RBCs at Baseline, Week 12 to Week 24, Week 24 to Week 36, and Week 12 to Week 36 will be presented by treatment arm. Additionally, separate boxplots showing the change from the 12-week prior to Baseline (Day 1) timeframe to the Week 12 to Week 24 and Week 24 to Week 36 time periods and from the estimated 24-week period prior to Baseline (Day 1) to the Week 12 to Week 36 time period will be presented by treatment group. The estimated 24-week period prior to Baseline (Day 1) is the same estimate as calculated for the hematological improvement secondary endpoint.

Proportion of Subjects who are Transfusion Independent for ≥8 Weeks During Treatment Endpoint

The number and percentage of subjects who remain transfusion independent for at least 8 weeks during treatment will be tabulated, along with summary statistics of the duration of transfusion independence in weeks. The proportion of subjects who are transfusion independent for at least 8 weeks during treatment will also be analyzed using CMH tests. ORs, 95% CIs, and p-values will be reported. The difference in proportions (active arm-Placebo and the combined active arms-Placebo) and corresponding 95% CI will be also provided.

Number of Transfusion Events Endpoint

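### SAP 13.6.4.1 compares a 24-week sum of transfused units with a 12-week baseline, and 13.6.6.1 cites a 24-week baseline estimate that is nowhere defined

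*SAP*

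**What the plan says.** SAP 13.6.4.1 defines improvement as a reduction of at least 20%, 33% or 50% in pRBC units, with a drop of at least 2 units. It is measured over fixed 12-week periods "or over 24 weeks (from Week 12 to Week 36) as compared to the 12-week period prior to the Baseline (Day 1) visit". The next sentence gives the quantity: "The pRBC units are defined as the sum all pRBCs units for the specific 12- or 24-week period".

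SAP 10.1.6, the section on the 24-week interval, sets the days: "Pre-treatment 12-week interval: from Day -83 to Day 1" and "Week 13–36 interval: from Day 86 to Day 253". It gives no pre-treatment interval other than the 12-week one.

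The endpoint lists (Protocol Table 1; SAP 6.1, 9.0 and Table 8; the bar-plot text in 13.6.4.1) name the 12 weeks before Baseline as the reference for Week 12–36 and do not mention scaling. Protocol Table 1 footnote a ties the 2-unit minimum to the same 12 weeks. Protocol 13.4.1 defines the response for 12-week periods only.

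SAP 13.6.6.1 pairs Week 12–36 with a 24-week pre-Baseline period in its boxplots of change in burden: "The estimated 24-week period prior to Baseline (Day 1) is the same estimate as calculated for the hematological improvement secondary endpoint". I found no such calculation in 13.6.4.1 or anywhere else in the two documents.

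SAP 13.6.4.1 also compares any 14-week rolling window with the 12 weeks before Baseline, at all three thresholds.

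**The concern.** A percentage reduction between two sums means what its label says only if the sums cover equal time. Here the treatment window is twice the baseline window, and the one passage that points to a matched baseline refers to a derivation that does not exist. A programmer who follows 13.6.4.1 and one who follows 13.6.6.1 will classify different patients as responders.

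Three Week 12–36 secondary endpoints are at stake, two of them (20% and 33%) taken from the protocol, together with the three 14-week rolling endpoints that the SAP added. Two exploratory endpoints inherit the ambiguity. One is the Week 12–36 mean change in burden (Protocol Table 1; SAP 9.0, Table 3 and Table 11). The other is the composite of a pre-transfusion Hb rise or a 33% reduction in burden (SAP 6.1, Table 3, Table 11 and 13.6.6.1).

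Timing matters too. In SAP Table 3 the Week 12–36 response is reported only at the final analysis, but SAP 12.0 lets blinded team members see group results from the interim analyses. A definition chosen after that could look data-driven.

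**Working it through.** The plan reports no figure for the Week 12–36 endpoint that could be reproduced. The 79% power in SAP 8.1.1 reproduces at 78.7% (normal approximation with continuity correction), but it names no time window and nothing below depends on it.

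**1. Window lengths** (SAP 10.1.5 to 10.1.8; 10.1.3 says there is no Day 0)
- Baseline, Day −83 to Day 1: 83 + 1 = 84 days
- Day 86 to 169 and Day 170 to 253: 84 days each
- Week 12–36, Day 86 to 253: 253 − 86 + 1 = 168 days
- 14-week rolling, e.g. Day 2 to 99: 98 days

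**2. Unchanged patient.** With B units per 12 weeks throughout, the 24-week sum is 2B and the reduction is 100 × (1 − 2B/B) = −100%, i.e. a doubling.

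**3. True rate cut needed.** With sums, a response at threshold t over W weeks requires W × new rate ≤ (1 − t) × 12 × old rate. The cut needed is therefore 1 − (1 − t) × 12/W.

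| Label | W = 12 | W = 14 | W = 24 |
|---|---|---|---|
| ≥20% | 20% | 31.4% | 60% |
| ≥33% | 33% | 42.6% | 66.5% |
| ≥50% | 50% | 57.1% | 75% |

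The sum sentence names only the 12- and 24-week periods. The 14-week column assumes the same treatment, because 13.6.4.1 says the rolling periods are analyzed similarly.

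**4. With the 2-unit minimum, whole units, B = 4 to 10** (TDT eligibility is >3 to 10 units). The literal ceiling is m = floor(min((1 − t)B, B − 2)), the same for 24 weeks as for 12, and the cut is 1 − m/(2B). With a doubled baseline the ceiling is floor(min((1 − t)2B, 2B − 2)) if the minimum is 2 units per 24 weeks, and floor(min((1 − t)2B, 2B − 4)) if it is 2 per 12 weeks. At the ≥20% label:

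| B | Literal 24-week ceiling | Cut needed | Doubled baseline, 2 per 24 weeks | Doubled baseline, 2 per 12 weeks |
|---|---|---|---|---|
| 4 | 2 | 75.0% | 6 | 4 |
| 5 | 3 | 70.0% | 8 | 6 |
| 6 | 4 | 66.7% | 9 | 8 |
| 7 | 5 | 64.3% | 11 | 10 |
| 8 | 6 | 62.5% | 12 | 12 |
| 9 | 7 | 61.1% | 14 | 14 |
| 10 | 8 | 60.0% | 16 | 16 |

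Literal cuts run from 66.7% to 75.0% at ≥33% and from 75.0% to 80.0% at ≥50%. The two readings of the 2-unit minimum differ at ≥20% for B = 4 to 7, at ≥33% only for B = 4 (5 against 4 units), and never at ≥50%.

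**5. Conflict with the half-periods.** Take a patient going from 8 units to 4 in Week 12–24 and 4 in Week 24–36. Each half gives 1 − 4/8 = 50%, a response at every label. Week 12–36 as written gives 1 − 8/8 = 0%, a non-response at every label. On equal lengths it is 1 − 8/16 = 50%.

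**6. Mean change, Week 12–36.** An unchanged patient scores 2B − B = +B, i.e. +4 to +10 units, against the 12-week reference and 2B − 2B = 0 against a 24-week one.

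**7. Does doubling the baseline suffice?** Take an unchanged patient at 8 units per 12 weeks who leaves at Day 169 with 8 units counted since Day 86. Doubling gives 1 − 8/16 = 50%, a response at all three labels with no change in rate. Units per 12 weeks of observed time gives 8 × 84/84 = 8, a 0% reduction. The case can arise: Protocol 8.5.1 withdraws subjects who stop study drug, SAP 13.6.3 plans no imputation, and SAP 11.4 can keep subjects who leave after Week 12 in the Per Protocol set.

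**The case against.** The best defence is that this is one missing sentence. Section 13.6.6.1 shows that a 24-week baseline was intended for this very endpoint, and validation would probably catch a definition under which an unchanged patient doubles. The intent is credible. However, the operative definition in 13.6.4.1 states a sum, and the cross-reference leads nowhere. Rescaling also leaves the 2-unit minimum and incomplete windows undecided, so a programmer cannot recover the rule from the text.

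Three narrower objections stand in full. First, only 13.6.4.1 states the sum. A reader might infer that Protocol Table 1 and the other endpoint lists require an unscaled comparison, but they name a reference period and are silent on scaling. Second, the sentence in 13.6.6.1 that summary statistics "during the 12-week period prior to Baseline (Day 1) and the 24-week post-Baseline time period will be provided" is not itself a contradiction: it describes two periods and computes no difference. Third, doubling the baseline would on its own introduce a new error for dropouts (step 7).

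A reader might also infer that the strict thresholds are deliberate. Nothing in either document says so, and 13.6.6.1 points the other way.

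**Conclusion.** The point holds. Read literally, 13.6.4.1 gives a wrong result for Week 12–36: labels of 20%, 33% and 50% stand for true rate cuts of at least 60%, 66.5% and 75%. It also conflicts with 13.6.6.1, so the two sections must be reconciled. The 14-week rolling endpoints share the fault on a smaller scale. The figures are arithmetic on the SAP's own windows; the whole-unit results also assume baselines of 4 to 10 whole units.

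A reader might infer that the error favours IMR-687. It does not: the same rule applies in every arm, and for fully observed windows the literal ceiling is always below the rescaled one, so responder counts can only fall or stay the same in each arm. Nor does it undermine the transfusion endpoints as a whole, since the fixed and rolling 12-week endpoints compare 84 days with 84 days. These are unadjusted secondary endpoints in a trial whose primary objective is safety. The point should be fixed before database lock, but it does not threaten the main conclusions.

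**What to change.** In SAP 10.1.6, 10.1.8 and 13.6.4.1:

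- Express both periods as pRBC units per 12 weeks. For a complete window, multiply the Week 12–36 sum by 84/168 and the 14-week sum by 84/98 before comparing with the Day −83 to Day 1 sum.
- State whether the minimum reduction of 2 units applies per 12 weeks or per window.
- State a rule for incompletely observed windows, for example non-responder if the window is not completed.
- Replace the cross-reference in 13.6.6.1 with this definition.

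Then align the entries that depend on it: the Week 12–36 and 14-week responses in SAP 6.1, 9.0, Table 8 and the 13.6.4.1 plots; the Week 12–36 mean change in SAP 9.0, Table 3 and Table 11; and the composite in SAP 6.1, Table 3, Table 11 and 13.6.6.1. Record the change in SAP 6.1 as a clarification of Protocol Table 1, which names the 12-week reference without a scaling rule.

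The cost is a few lines of derivation and wording. No new data are needed, and SAP 6.0 already foresees updates before database lock.

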8.2 Randomization

All subjects who are screened (including screen failures) will be assigned a unique subject identification number.

On Day 1, eligible subjects in Population 1 (TDT Population) and Population 2 (NTDT Population) will be assigned another unique number (randomization number) in sequential order. The randomization number codes the subject's initial treatment assignment according to the randomization schedule generated prior to the study. Initially, subjects will be randomly assigned in a 2:1 ratio to receive either IMR-687 lower dose or placebo. If the DMC recommends inclusion of the higher dose, randomization will then proceed in a 1:2:1 ratio (IMR-687 lower dose, IMR-687 higher dose, or placebo).

Randomization schedules will be generated by Cytel, a subcontractor of the IXRS vendor Suvoda.

Subject randomization will be stratified by TDT/NTDT status.

Randomization number will not be reused once assigned. If a subject discontinues or is discontinued at the discretion of the investigator or DMC up to and including the Week 12 visit, the subject may be replaced with another subject, from the same TDT/NTDT stratum, meeting the eligibility criteria. In the event that a subject is replaced, the replacement subject will receive the same treatment as the replaced subject, and a different leading number will be used for the replacement randomization. Subjects who are replaced, or who are replacement subjects, will be included in the analyses sets according to the same criteria used for all other subjects, as described in Section 11.0.

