10.1.5 Red Blood Cell Transfusion Reduction: 12-Week Fixed Interval

Transfusion burden will be measured using a “fixed” 12-week time interval. The 12-week intervals used for analysis are defined as:

Pre-treatment 12-week interval: from Day -83 to Day 1;

Week 13–24 interval: from Day 86 to Day 169;

Week 25–36 interval: from Day 170 to Day 253.

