10.1.7 Red Blood Cell Transfusion Reduction: 12-Week Rolling Interval

Transfusion reduction will also be measured using any consecutive “rolling” 12-week time intervals during the study, e.g., Days 2 to 85, Day 3 to 86 and so on, compared to the pre-treatment 12-week interval (from Day-83 to Day 1). A transfusion occurring on Day 1 belongs to the pre-treatment period.

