11.4 Per Protocol Analysis Set

The Per Protocol Analysis Set will include all subjects in the Safety Analysis Set who have provided sufficient data without major protocol deviations or events that would be expected to affect the analysis. Sufficient data is defined as any post-baseline assessment and subject did not discontinue prior to week 12 for reasons other than AEs. The PP Analysis Set will be identified based on blinded data prior to unblinding the final analysis dataset, and the TDT and NTDT populations may have their PP Analysis Set components defined at different times. The PP Analysis Set will be the primary analysis set used for PD and efficacy analyses. Subjects will be analyzed according to their randomized treatment.

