13.0 Statistical Methods

All statistical analyses will be conducted using SAS Version 9.4.

Descriptive summary statistics will be provided for demographics, disposition, and IMR-687 exposure. The number and percentage of subjects who discontinue from the study, along with reasons for discontinuation will be tabulated.

Continuous data will be summarized using descriptive statistics (number of subjects, mean, SD, median, first quartile (Q1), third quartile (Q3), minimum, and maximum, %CV). Frequencies and percentages will be used for summarizing categorical (discrete) data. For summaries of categorical variables, counts and percentages are based on the number of subjects in the analysis set unless otherwise specified.

All statistical tests and resulting p-values will be reported as 2-sided. Confidence intervals, when presented, will be constructed at the two-sided 95% level, unless noted otherwise.

P-values will be presented to 4 decimal places with values less than 0.0001 presented as “<0.0001” and p-values greater than 0.9999 presented as “>0.9999”.

Means, medians, Q1s, and Q3s will be presented to 1 or more decimal places than the recorded data. The SDs will be presented to 2 more decimal places than the recorded data. Confidence intervals about a parameter estimate, minimums, and maximums will be presented using the same number of decimal places as the parameter estimate. Percentages will be presented to 1 decimal place.

A month is operationally defined to be 30.4375 days. A year is defined to be 365.25 days. A week is defined to be 7 days.

Where specified, there will be pair-wise comparisons between IMR-687 lower dose vs. placebo, IMR-687 higher dose vs. placebo and IMR-687 pooled dose vs. placebo.

Separate table and figure outputs will be produced for each TDT/NTDT population. The TDT population may be unblinded and reported at a separate time from the NTDT population depending on enrollment. If this occurs the blind of the unfinished population will be preserved. Listings will include both the TDT and NTDT populations with the TDT population presented first in the listing

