13.6.3 Imputation Methods for Endpoints

Unless otherwise specified, no imputation of data relating to the primary endpoint of safety and tolerability, or for secondary or exploratory efficacy endpoints, will be performed.

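### SAP 13.6.4.1 has no rule for unobserved time in the TDT transfusion endpoints, so early leavers can be read as responders and short follow-up as fewer transfusions

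*SAP*

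**What the plan says.** **Windows.** SAP 10.1.5 and 10.1.6 fix the windows by study day: Day 86 to 169, the Week 25-36 "interval: from Day 170 to Day 253", and Day 86 to 253 for the 24-week comparison. SAP 10.1.7 adds rolling "12-week time intervals during the study, e.g., Days 2 to 85, Day 3 to 86 and so on"; SAP 10.1.8 does the same for 14 weeks.

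**Scoring (SAP 13.6.4.1).** Burden is a plain sum: "The pRBC units are defined as the sum all pRBCs units for the specific 12- or 24-week period". For rolling windows, "a responder is defined as a subject who meets the hematological improvement criteria in at least one of the rolling time periods". The number of transfusion events is a cumulative count to Week 36, compared by ANCOVA with baseline value and treatment only.

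**Missing data.** Unless specified elsewhere, "no imputation of data relating to the primary endpoint of safety and tolerability, or for secondary or exploratory efficacy endpoints, will be performed" (SAP 13.6.3). For summaries of categorical variables, "counts and percentages are based on the number of subjects in the analysis set unless otherwise specified" (SAP 13.0).

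**Who stays in.** Protocol 8.5.1 requires a patient who stops study drug to be withdrawn. The Per Protocol (PP) set is primary for efficacy (SAP 11.4): "Sufficient data is defined as any post-baseline assessment and subject did not discontinue prior to week 12 for reasons other than AEs". ITT keeps everyone randomized (SAP 11.2). Replaced subjects and their replacements "will be included in the analyses sets according to the same criteria used for all other subjects" (SAP 8.2).

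**Contrast.** Early discontinuation is handled for chelation dose and ferritin (SAP 13.6.4.1), and transfusion and missing values are handled for NTDT Hb and HbF (SAP 13.6.4.2). The TDT transfusion endpoints have no equivalent.

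**The concern.** Transfusion records stop when a patient leaves, so a plain sum over a calendar window falls for a reason that has nothing to do with transfusion need. TDT entry requires more than 3 units in 12 weeks (Protocol 8.1). A patient with no recorded units in a 12-week window therefore shows a 100% reduction of at least 4 whole units, which meets the 20%, 33%, 50% and 2-unit criteria together. In the rolling analysis one such window is enough. In the event analysis a short record looks like a low count.

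Three readings of the same data (sum what was recorded, set to missing, score as non-responder) give different response rates. The SAP leaves that choice to whoever programs the tables. If the sum is used, response is overstated in every arm with dropout, a true effect is diluted, and an arm that loses clearly more patients gains a spurious advantage.

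The interims have a related gap. SAP Section 12, Table 3, lists Week 12 to 24 response for IA 1.0, and no text limits that table to patients whose window has ended.

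**Working it through.** **1. The plan's own figure.** SAP 8.1.1: 30 versus 20, 50% versus 10%, two-sided 0.05, about 79% power. Normal approximation with continuity correction: pooled rate (30×0.5 + 20×0.1)/50 = 0.34; null SE 0.1367; alternative SE 0.1133; correction 0.5×(1/30 + 1/20) = 0.0417. Power = Φ[(0.40 − 0.0417 − 1.96×0.1367)/0.1133] = 78.7%. The planned one-stratum CMH test, by exact enumeration of two binomials, has 88% power. That is the reference below.

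**2. One patient with no true change.** Assume 2 units every 21 days (Days 14, 35, … 245) and a baseline of 8 units.
- Completes: 8 units in each 12-week window, no response; 12 events.
- Leaves Day 85: 0 units in Day 86-169, responder at 20%, 33% and 50%; 4 events.
- Leaves Day 120: 4 units, a 50% reduction, responder at all three.
- Leaves Day 140: 6 units, a 25% reduction of 2 units, responder at 20%.
- Leaves Day 200: 2 units in Day 170-253, so a rolling responder at all three.

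**3. Share of no-effect leavers scored as ≥20% responders.** Simulated histories over four transfusion patterns, with the last recorded day uniform on Day 29-253 (225 days) and unrecorded days contributing nothing: 57-61% for Week 12-24 and 91-92% for Week 24-36, against 13-18% when fully observed. Rolling 12-week ≥50%, base pattern (mean interval 21 days, SD 2, mostly 2-unit events): 83%, against 6.5% fully observed and 3% if only windows that ended by the last recorded day count.

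**4. False positives under the literal sum.** Let p be the true response (10%, the SAP's placebo rate). Leavers before the window score 1, within it 0.79 (simulated), after it p. Mean leaver score L:
- Week 12-24: 57/225 + 0.79×83/225 + 0.10×85/225 = 0.583
- Week 24-36: 141/225 + 0.79×83/225 + 0.10×1/225 = 0.919

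Arm rate = (1 − d)p + dL for dropout d. Exact CMH rejection, n = 30/20, no drug effect:

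| Dropout active/placebo (%) | Wk 12-24 scored rates (%) | Rejection | Wk 24-36 scored rates (%) | Rejection |
|---|---|---|---|---|
| 0/0 | 10.0/10.0 | 3.2% | 10.0/10.0 | 3.2% |
| 10/10 | 14.8/14.8 | 3.9% | 18.2/18.2 | 4.2% |
| 10/5 | 14.8/12.4 | 3.8% | 18.2/14.1 | 4.8% |
| 15/5 | 17.2/12.4 | 5.1% | 22.3/14.1 | 8.4% |
| 25/5 | 22.1/12.4 | 10.5% | 30.5/14.1 | 23.5% |

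At 20/20 it also stays below 5%. Rolling ≥50% (completers 6.5%, leavers 83%): 4.1%, 7.8% and 22.6% at 10/5, 15/5 and 25/5. With non-responder scoring, no unequal scenario for the fixed windows exceeds 4.3%.

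**5. Power, 50% versus 10%, at 10/10.**

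| Reading | Wk 12-24 | Wk 24-36 |
|---|---|---|
| Literal sum | 81% | 76% |
| Non-responder | 85% | 82% |
| Missing | 86% | 85% |

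Scoring active leavers within the window at 0.895 instead of 0.79 moves the first row by at most 1 point.

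**6. Event counts.** A leaver's mean last day is (29 + 253)/2 = 141, so 112 days are unobserved, or 112/21 = 5.33 events. Bias = −5.33 × (active − placebo dropout): −0.3, −0.5 and −1.1 events at 10/5, 15/5 and 25/5. Simulated ANCOVA rejection with no drug effect is 3.2%, 7.5% and 29%. A quasi-Poisson model with log observed days as offset and log baseline count as covariate gives a rate ratio of 1.00 and 4-5% rejection.

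**The case against.** **Zero is not stated.** No sentence says that unobserved days count as zero units. The response definition refers to a reduction over a fixed span, the rolling text refers to intervals during the study, and imputation is barred; counting unobserved days as zero could itself be called imputation. This stands. A reader might infer that the SAP orders early leavers to be scored as responders, and the text does not support that. It supports the narrower point that the literal sum permits it and no alternative is chosen. The sentence on denominators does not settle it either, since it does not say how an unevaluable patient is scored.

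**PP is primary.** It drops non-AE leavers before Week 12, replaced ones included, and blinded review may drop more. The tables above drop no one, so they describe ITT. If 0-50% of pre-Week-12 leavers left for an AE (an assumption), 25/5 gives about 8-9% for Week 12-24 and 19-20.5% for Week 24-36: lower, but still raised. A reader might infer that replaced subjects always remain in PP; SAP 8.2 only applies the usual criteria to them.

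**The large figures need strongly unequal dropout.** This also stands. Nothing in the documents supports 25% versus 5%, and at 10/5 there is no material inflation. The null rate matters too: using the simulated 15.5% in place of 10%, 25/5 gives 9.3% and 19.6%.

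**Interims.** Restricting tables to patients with 24 weeks completed is a natural reading of the milestone, but it is unstated.

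**Conclusion.** The gap is real and should be fixed before unblinding. For TDT patients who leave before or during a window, the SAP gives no scoring rule. The literal sum can make them responders, and the event ANCOVA takes no account of follow-up. AE leavers before Week 12 and anyone leaving later stay in PP by default; ITT keeps all.

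The size depends on assumed dropout spread evenly over Day 29-253. The firm consequence is overstated response in every arm with dropout, and lost power even when dropout is equal (88% to 81% or 76% at 10/10). Inflated false positives are conditional: they need clearly more dropout on active, and they are worse for Week 24-36 than for Week 12-24. A general claim that the type I error is inflated is not supported.

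These are secondary endpoints in a study whose primary objective is safety, tested without multiplicity adjustment, so the point does not threaten the primary analysis. Moving from PP to ITT would not cure it, because the scoring rule is the problem.

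**What to change.** 1. **Response (SAP 13.6.4.1, PP and ITT/mITT).** State that a patient who withdraws before the end of a fixed window is a non-responder for that window, with setting the window to missing as a sensitivity analysis. Treat a patient who completes the Week 24 or Week 36 visit within its protocol visit window as having completed the matching window. This allowance is needed because Week 36 is Day 252 ± 7, so 8 of its 15 permitted days (245-252) fall before Day 253. Its residual effect is small: with no Week 40 record, no-effect completers score 20% instead of 15.5% at ≥20% for Week 24-36. Count a rolling window only if it ends on or before the last day with recorded transfusion data.
2. **Events.** Replace the ANCOVA with a quasi-Poisson model: log observed days as offset, log baseline count as covariate.
3. **Interims.** Include every patient whose window would have ended by the data cut-off counting from their own Day 1, whether or not they withdrew. Do not add early withdrawals whose window would not yet have ended: their still-enrolled contemporaries are excluded, so adding them would introduce bias.

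**Cost.** SAP wording and programming only. Reported response rates will fall. Non-responder scoring also works against an arm with more dropout: at 10/5, 15/5 and 25/5, power for 50% versus 10% is 84%, 81% and 74% (Week 12-24) or 81%, 75% and 62% (Week 24-36), from 88% with none. Setting windows to missing keeps more power at 10/10, but it relies on leaving being unrelated to response, which is why it is better placed as the sensitivity analysis.
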